## **6.0 STRATIFICATION/DESCRIPTIVE FACTORS/RANDOMIZATION SCHEME**

This is a prospective, single institution, controlled, pilot study of patients admitted to the 7W ICU. A sample size of 104 (52 per group) is targeted. Patients will be screened for study eligibility on a daily basis. The control group will undergo standard ICU care, which includes the use of the ABCDEF bundle (Appendix 1) daily, which involves delirium screening using the CAM-ICU tool (Appendix 2), but will not have routine psychiatric involvement in care. Enrollment and data collection will continue for as long as it takes to reach the target sample size of 52 patients for this group. We will then proceed to enroll patients into the intervention group, who undergo standard care (including ABCDEF bundle implementation, which is standard practice in 7W ICU) in addition to a psychiatric team intervention, which entails having a member of the psychiatric team (attending, resident, and/or fellow) participate in daily (Monday-Friday) multidisciplinary rounds with the ICU team; they will help provide nonpharmacological and pharmacological intervention strategies in patients diagnosed with delirium and help distinguish delirium from other psychiatric disorders which may be missed by the ICU team and provide earlier treatment of these conditions. This study phase will continue until the target sample size of 52 patients is reached.

Data will be collected for both the control and intervention groups (see Section 12) and compared.

Randomization is not possible for this study; although block randomization was considered, it will result in sub-optimal data subject to bias.

## **7.0 STUDY AGENT ADMINISTRATION OR INTERVENTION AND TOXICITY MANAGEMENT PLAN**

In addition to standard care (ABCDEF bundle, which includes daily CAM-ICU screening for Delirium by ICU nurses), the intervention will be daily multidisciplinary ICU rounds with a psychiatry team member, who will collaborate with the ICU team in implementing preventative strategies, assist in the pharmacological and nonpharmacological treatment of patients with delirium, and assist in differentiating delirium from other psychiatric disorders which may not be detected by ICU providers, thus, identifying, addressing, and treating these illnesses at an earlier time.

## **8.0 ASSESSMENT OF EFFICACY AND SAFETY**

Not applicable

## **9.0 CLINICAL AND LABORATORY EVALUATIONS AND STUDY CALENDAR**

We will collect basic demographic data and screen for delirium using the CAM-ICU (which is standard practice in the ICU). The ABCDEF bundle and CAM-ICU screening tool are performed by the ICU nurses on a daily basis in the morning. The CAM-ICU may be performed later on in the day if the patient's mental status changes. The findings in the ABCDEF bundle and CAM-ICU screening tool are communicated to the ICU team on morning rounds. In patients who develop delirium, we will

collect data on their total ICU/hospital LOS (length of stay), days on mechanical ventilation (if applicable), duration of delirium, and in-hospital mortality.

No additional laboratory studies or investigative studies will be performed for the study.

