## **2.0 OBJECTIVES AND PURPOSE**

The purpose of our study is to determine the effect of delirium prevention care bundle protocols, and a multi-disciplinary care model rounding with a psychiatry team (intervention group) on ICU delirium and patient outcomes as compared to a group undergoing standard care without routine psychiatry team participating in ICU rounds (control group). Since the incidence of ICU delirium is so high and it has negative ramifications on patient survival, long-term outcomes, cognitive function, and places a heavy burden on the healthcare system and cost, preventative strategies are desperately needed. Using bundle care protocols and multidisciplinary rounding with psychiatry may be a feasible and cheap measure to help prevent delirium in ICU patients.

The primary objective is the incidence of ICU delirium.

The secondary objectives are:

- duration of delirium
- ICU and hospital length of stay
- days of mechanical ventilation (if applicable)
- in-hospital mortality

Our primary hypothesis is that the intervention of psychiatry team participation in multidisciplinary ICU rounds with the surgical ICU team will result in a decreased incidence of delirium compared to standard care without routine psychiatry team involvement. Our secondary hypothesis is that psychiatric team participation in multidisciplinary ICU rounds will decrease delirium duration, decrease ICU and hospital length of stay, decrease mechanical ventilation duration, and decrease in-hospital mortality compared to the standard care group.

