The control group will receive standard care, including the use of the ABCDEF bundle (Appendix 1) daily, which involves delirium screening using the Confusion Assessment Method-Intensive Care Unit (CAM-ICU) score (Appendix 2), but will not have routine psychiatric involvement in care. The CAM-ICU is performed by the ICU nurses on a daily basis. It consists of several questions that assess patient's mental status, if the change in mental status fluctuates, the sedation score (using Richmond Agitation Sedation Score [RASS]), and the patient's attention span and if disorganized thinking is present by asking several questions. The CAM-ICU can be performed in intubated patients by asking the patient to follow commands with their hands, or squeeze the nurse's hand in response to a question. The CAM-ICU will be done every morning, but may also be repeated later on in the day if the patient's mental status changes from the morning-this will be the same for both the control and intervention group. Enrollment and data collection will continue for as long as it takes to reach the target sample size of 52 patients for this group. We will then provide standard care (including ABCDEF bundle implementation, which is standard practice in 7W ICU) and provide routine psychiatric care, which entails a member of the psychiatric team (attending, resident, and/or fellow) participating in daily (Monday-Friday) multidisciplinary rounds with the ICU team (intervention group); the psychiatry team will help provide nonpharmacological and pharmacological intervention strategies in patients diagnosed with delirium and help distinguish delirium from other psychiatric disorders which may be missed by the ICU team and provide earlier treatment of these conditions. This study phase will continue until the target sample size of 52 patients is reached.

In both the control and intervention groups, delirium will be diagnosed by a positive CAM-ICU score. Both groups will have the CAM-ICU test administered by the patient's nurse on a daily basis (which is standard practice in 7W ICU) in the morning and may be repeated later on in the day if the patient's mental status changes. Data on the incidence of ICU delirium, duration of delirium/mechanical ventilation, in-house mortality, hospital and ICU length of stay will be collected.

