Additionally, we will collect the following data: age, gender, body mass index, history of alcohol or substance abuse, admitting diagnosis, dementia, comorbid conditions, admitting Sequential Organ Failure Assessment (SOFA) score, deliriogenic medications used during study enrollment, the interventions/medications used to treat delirium as designated by psychiatry and the ICU team (in intervention group) and the ICU team (control group), and the number of days from ICU admission to study enrollment. We will input data into a secure, password protected, encrypted, electronic database, RedCap.

The data points will be compared between the control and intervention groups (see section 13.0).

Our primary outcome is: incidence of ICU delirium.

The secondary outcomes are: duration of delirium/mechanical ventilation, in-house mortality, and hospital and ICU length of stay.

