## **12. DATA COLLECTION AND MONITORING**

Data which will be collected includes: age, gender, body mass index, history or alcohol or substance abuse, admitting diagnosis, dementia, comorbid conditions, admitting Sequential Organ Failure Assessment (SOFA) score, deliriogenic medications used during study enrollment, the interventions/medications used to treat delirium as designated by psychiatry in conjunction with the ICU team (in intervention group) and the ICU team (control group), and the number of days from ICU admission to study enrollment. Data on the incidence of ICU delirium, duration of delirium/mechanical ventilation, in-house mortality, and length of stay will also be collected.

Data will be collected using RedCap, a password protected website. No patient identifiers will be used. A copy of the information sheet will be provided to the patient and be placed in the patient's chart. We will retain a copy of the information sheet in a double locked storage office.

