characteristics between the 2 groups. The incidence of delirium will be compared using  $\chi^2$  test and multivariable logistic regression. Differences in the duration of delirium and MV between the intervention and control groups will be analyzed by analysis of variance (ANOVA). The length of stay will be compared by truncated negative binomial regression, while mortality rates will be compared via logistic regression. A sensitivity analysis will be performed in order to assess the possible confounding effect of the non-randomized nature of our study design. A propensity score model for receipt of standard care vs. psychiatric involvement will be performed in order to approximate a balanced covariate distribution between the 2 groups as that would be expected by randomization. We will then use the propensity score for each subject to perform an inverse probability weighted comparison of the groups on our trial outcomes.

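### Section 9 ties collection of length of stay, ventilation days and in-hospital mortality to patients who develop delirium, at odds with the rest of the plan

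*Combined protocol and SAP*

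**What the plan says.** Section 9, the section on evaluations and the study calendar, begins its sentence on outcome data with "In patients who develop delirium, we will" and continues "collect data on their total ICU/hospital LOS (length of stay), days on mechanical ventilation (if applicable), duration of delirium, and in-hospital mortality". As written, all four items hang on the patient having become delirious.

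The other sections carry no such condition:

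- **Section 3** closes a paragraph about both groups with "Data on the incidence of ICU delirium, duration of delirium/mechanical ventilation, in-house mortality, hospital and ICU length of stay will be collected". It then says that the collected items are compared between the control and intervention groups.
- **Section 6** says that data are collected for both groups and compared, and refers to Section 12 for the list.
- **Section 10** lists the same secondary outcomes without restriction.
- **Section 12** says "Data on the incidence of ICU delirium, duration of delirium/mechanical ventilation, in-house mortality, and length of stay will also be collected".

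The objectives and the analysis also refer to groups. Section 2 states: "Our secondary hypothesis is that psychiatric team participation in multidisciplinary ICU rounds will decrease delirium duration, decrease ICU and hospital length of stay", and goes on to ventilation time and in-hospital mortality, all relative to the standard care group. Section 13 states: "The length of stay will be compared by truncated negative binomial regression, while mortality rates will be compared via logistic regression". For the sensitivity analysis it adds: "We will then use the propensity score for each subject to perform an inverse probability weighted comparison of the groups on our trial outcomes". It names no delirious-only subset.

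**The concern.** Delirium is the primary outcome, and it arises after the intervention has begun. If length of stay, ventilation days and mortality are recorded only in patients who become delirious, these outcomes are conditioned on the very event the intervention is meant to prevent. A patient whose delirium is prevented drops out of the secondary data, and so does any benefit that patient gains. The delirious patients left in the two groups need not be alike. The result would not answer the Section 2 hypothesis.

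The order of enrolment adds a practical risk. Sections 3 and 6 fill the control group first and the intervention group second. If staff read the two rules differently at different times, the groups could be collected under different rules.

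**Working it through.** **1. Can the sections be reconciled?** Delirium duration applies naturally to delirious patients, so the Section 9 condition fits that one item. It does not fit the other three, which exist for every patient or every ventilated patient. Section 6 points to Section 12 for the data list, and that list is unconditional. So the intended denominator can be inferred as both whole groups. However, no section says in terms that these outcomes are recorded for all enrolled patients, and Section 9 is the only place that attaches a patient-level condition to them. No passage resolves the difference.

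**2. Inputs, all from Section 13.** Control incidence is roughly 40%. A large effect is put at a 25% reduction. There are 47 evaluable patients per group, 94 in all. The plan's 95% interval for the difference is 8%-42%.

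**3. The plan's own figure.** Reading the 25% as percentage points gives 40% versus 15%:

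0.25 ± 1.96 × √[(0.40 × 0.60 + 0.15 × 0.85) / 47] = 0.25 ± 0.173, or 7.7% to 42.3%.

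This matches 8%-42%, so the absolute reading is the one behind the plan's interval. The relative reading (40% versus 30%) gives 0.10 ± 0.192, or -9.2% to 29.2%, which does not match. I carry it below only as the less favourable case.

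**4. Patients with secondary data if Section 9 is followed literally.** Expected number = 47 × incidence.

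| Scenario | Control | Intervention | Total | Share of 94 |
|---|---|---|---|---|
| 40% vs 15% | 18.8 | 7.05 | 25.85 (about 26) | 27.5% |
| 40% vs 30% | 18.8 | 14.1 | 32.9 (about 33) | 35.0% |
| Sections 3 and 12 | 47 | 47 | 94 | 100% |

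**5. What the subset can show.** Let p be the incidence of delirium, and let D and N be the mean outcome with and without delirium. A group mean is p × D + (1 - p) × N. Suppose the intervention changes only p, with prevented cases a random sample of delirious patients who take on the outcome N. The whole-group difference is then (difference in p) × (D - N), that is 0.25 × (D - N) or 0.10 × (D - N). Among delirious patients it is D - D = 0, so the benefit disappears from view.

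If prevented cases are not a random sample, the subset comparison is biased as well. If the milder cases are prevented, the remaining delirious intervention patients are sicker on average and the intervention looks worse. If the more severe cases are prevented, it looks better. The documents give no basis for choosing between these.

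**6. The weighted analysis.** Propensity weights built to balance the whole groups need not balance the delirious subset. A weighted comparison could still be computed there, but it would not estimate the planned whole-group effect.

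**The case against.** The best defence is that Section 9 is a summary and not the controlling rule. It mentions only basic demographics, CAM-ICU screening and outcomes. It omits the SOFA score, comorbid conditions, deliriogenic medications and days from ICU admission to enrolment, all of which Sections 3 and 12 require, and nobody would conclude that those are not collected. It does not contain the word *only*. Section 6 sends the reader to Section 12, and Sections 2, 3, 10 and 13 point the same way. The items are routine chart data, so an omission might be recoverable. The pilot is sized on delirium incidence and not on these outcomes.

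Most of this stands, and it limits the point. A reader might infer that the trial will in fact lose these outcomes for everyone without delirium. The documents do not support that; they support a conflict of wording whose likely resolution is whole groups. A reader might also try to count the deaths that would be missed. Section 1 gives in-hospital mortality with delirium, but its 2-3 times risk ratio is for death during the ICU stay, and no in-hospital mortality without delirium is given. Any such count would rest on an unsupported assumption, so none is offered.

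What the defence does not do is remove the contradiction. A study calendar section is a natural place for staff to look for what to record on whom, and its plain reading restricts collection.

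**Conclusion.** The contradiction is real and should be fixed. Section 9, read as written, gives a rule for length of stay, ventilation days and in-hospital mortality that conflicts with Sections 2, 3, 6, 10, 12 and 13. Followed literally, it would leave these outcomes for about 26 of 94 patients at 40% versus 15%, or about 33 of 94 at 40% versus 30%. Those figures rest on the plan's incidence assumptions and on 94 evaluable patients. The subset comparison would miss benefit that works through prevention, could be biased either way, and would not test the stated hypothesis.

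Confidence in the textual conflict is high. Whether data would actually be lost is not established, and loose drafting around delirium duration is a plausible explanation. The primary outcome, its interval and the sample size are unaffected.

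**What to change.** Reword the Section 9 sentence along these lines: *For every enrolled patient in both groups we will record ICU and hospital length of stay, ventilation days (if applicable) and in-hospital mortality; for patients who develop delirium we will also record its duration.*

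Add to Section 13: *Length of stay and in-hospital mortality are compared in all enrolled patients. Any comparison limited to patients with delirium is labelled as conditional on delirium.*

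The cost is a sentence in Section 9 and a line or two in Section 13. There is no new data item, because Sections 3 and 12 already list them. The wording secures them for the roughly 61 to 68 of 94 patients expected to stay free of delirium (94 - 32.9 = 61.1; 94 - 25.85 = 68.15). The sample size, primary analysis and planned models stay as they are.

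A separate clarification can be made in the same edit: Section 13 does not say whether patients without delirium, or never ventilated, count as zero days or are left out of the duration comparisons. That gap would remain after Section 9 is corrected and does not carry this point.

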## **10.0 CRITERIA FOR EVALUATION AND ENDPOINT DEFINITIONS**

Primary outcome: incidence of delirium, defined by a positive CAM-ICU.

Secondary outcomes: delirium duration, ICU/hospital length of stay, in-hospital mortality, and mechanical ventilation duration.

## **11.0 SPECIAL INSTRUCTIONS:**

Not applicable

## **12. DATA COLLECTION AND MONITORING**

Data which will be collected includes: age, gender, body mass index, history or alcohol or substance abuse, admitting diagnosis, dementia, comorbid conditions, admitting Sequential Organ Failure Assessment (SOFA) score, deliriogenic medications used during study enrollment, the interventions/medications used to treat delirium as designated by psychiatry in conjunction with the ICU team (in intervention group) and the ICU team (control group), and the number of days from ICU admission to study enrollment. Data on the incidence of ICU delirium, duration of delirium/mechanical ventilation, in-house mortality, and length of stay will also be collected.

Data will be collected using RedCap, a password protected website. No patient identifiers will be used. A copy of the information sheet will be provided to the patient and be placed in the patient's chart. We will retain a copy of the information sheet in a double locked storage office.

## **13.0 STATISTICAL CONSIDERATIONS**

In this pilot study, sample size considerations were based on obtaining sufficient patient numbers to assess feasibility of the intervention and data collection on the surgical unit, as well as to obtain estimates of incidence of delirium in the current care model (the base incidence) and the magnitude of effect of introduction of psychiatric involvement on the unit. All of these data are required for determination of feasibility of and sample size estimation for a larger definitive trial that would likely be a multi-centered cluster randomized trial. Based on our clinical experience in the 7W ICU, the incidence of delirium over the past year was roughly 40%; from the literature, a large intervention effect would be on the order of 25% reduction in incident delirium. We used these initial approximations to determine the precision (i.e., width of a 95% confidence interval) with which we can estimate these two parameters for use in future trial planning. Given a sample size of 94 patients (47 in each group), we will be able to estimate the actual difference in the incidence of delirium in our proposed intervention group (compared to SOC) with a precision (95% confidence interval) of 8%-42%. In the 47 in the SOC group, we will be able to estimate the base rate of delirium incidence with a 95% confidence interval of 26%-55%. The effect size and base rate estimated from this pilot trial will help us design future multi-center, larger population studies.

A sample size of 104 will be targeted to account for a 10% drop-out rate.

Descriptive statistics, including Student's t-test or Mann-Whitney U-test, for continuous variables and  $\chi^2$  or Fisher's exact test, for categorical variables, will be used to summarize the data and compare

characteristics between the 2 groups. The incidence of delirium will be compared using  $\chi^2$  test and multivariable logistic regression. Differences in the duration of delirium and MV between the intervention and control groups will be analyzed by analysis of variance (ANOVA). The length of stay will be compared by truncated negative binomial regression, while mortality rates will be compared via logistic regression. A sensitivity analysis will be performed in order to assess the possible confounding effect of the non-randomized nature of our study design. A propensity score model for receipt of standard care vs. psychiatric involvement will be performed in order to approximate a balanced covariate distribution between the 2 groups as that would be expected by randomization. We will then use the propensity score for each subject to perform an inverse probability weighted comparison of the groups on our trial outcomes.

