## **1.0 BACKGROUND AND HYPOTHESIS**

We are interested in evaluating a multifaceted prevention protocol for ICU delirium. Delirium affects 45-80% of elderly ICU patients, 60-80% of mechanically ventilated ICU patients, and 20-50% of non-mechanically ventilated ICU patients (1-4). About 30-40% of cases are preventable (1, 2). Without routine screening, delirium is often undiagnosed (5-7). Numerous studies have consistently shown that ICU delirium is associated with a worse prognosis (8). The annual cost of delirium and its ramifications in the U.S., is estimated to be \$4-16 billion (1).

Delirium impacts emotional well-being, as delirious patients experienced delusional memories and had less factual recall than non-delirious patients (9-11). A meta-analysis performed by Zhang et al. found delirium to be associated with a higher mortality rate, longer ICU and hospital lengths of stay, longer duration of mechanical ventilation, and higher probability of discharge to a skilled placement facility. (9) ICU-acquired delirium is independently associated with increased cognitive and physical impairment and health care costs (6, 12). Delirium was also found to be associated with more complications (9,13). Patients who develop delirium have a 2-3 times increased risk of dying during ICU admission (8, 14), with ICU mortality ranging from 1-16% (15-17), and an in-hospital mortality rate of 25% to 33%. (12, 18). It is also associated with increased hospital length of stay (13, 19) and each additional day of delirium increases post-discharge mortality up to a year after discharge (14, 16, 19).

Patients with ICU delirium had a higher incidence of cognitive impairment at hospital discharge, and up to 18 months post-discharge (20, 21) A longer duration of delirium in the hospital was associated with worse global cognition and executive function scores at 3 and 12 months (22), and it is associated with the development of new-onset dementia, or worsening of existing dementia (2, 22). In addition to cognitive problems, delirium was found to be associated with more problems in activities of daily living and worse scores on sensorimotor function tests at follow-up (3). Anxiety, depression, and posttraumatic stress disorder are common in survivors of critical illness (20, 21).

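### Section 9 limits delirium duration and other secondary outcomes to patients who become delirious, Sections 3 and 12 do not, and the ANOVA in Section 13 has no rule for patients without delirium or for death

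*Combined protocol and SAP*

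**What the plan says.** Section 2 hypothesises that psychiatry participation in rounds "will decrease delirium duration, decrease ICU and hospital length of stay, decrease mechanical ventilation duration, and decrease in-hospital mortality", alongside a lower incidence of delirium. Section 10 names the secondary outcomes but gives no start, stop, unit or window for either duration. Section 13 then states: "Differences in the duration of delirium and MV between the intervention and control groups will be analyzed by analysis of variance (ANOVA". It does not say which patients enter that comparison, what value a patient without delirium receives, or what happens at death or ICU discharge.

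The sections disagree on who contributes data. Section 9 opens its sentence on the secondary outcomes with "In patients who develop delirium, we will" and goes on to "collect data on their total ICU/hospital LOS (length of stay), days on mechanical ventilation (if applicable), duration of delirium, and in-hospital mortality". Section 12 has no such limit: "Data on the incidence of ICU delirium, duration of delirium/mechanical ventilation, in-house mortality, and length of stay will also be collected". Section 3 also lists these outcomes without restriction.

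On measurement, Section 3 says "In both the control and intervention groups, delirium will be diagnosed by a positive CAM-ICU score" and "The CAM-ICU is performed by the ICU nurses on a daily basis". The test is done each morning and may be repeated if mental status changes. No delirium assessment outside the ICU is described.

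**The concern.** Becoming delirious is the primary outcome, and it happens after enrolment. A comparison of durations among delirious patients only is therefore made in a subset that the intervention is meant to shrink. If the prevented episodes are mainly the short ones, those that remain are longer on average, and an intervention that works appears to prolong delirium. If Section 9 is followed, the same selection applies to ventilation days, length of stay and mortality.

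Death is a second problem. Without a rule, a patient who dies while delirious or ventilated contributes a short duration, which reads as a good result, although lower mortality is itself hypothesised.

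Section 13 says the pilot's estimates will inform a larger multi-centre trial, so a duration estimate with the wrong sign could be carried forward.

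**Working it through.** **The plan's own figures.** The plan gives no figure for duration. Its interval for the difference in incidence fixes the two incidences it has in mind. With 47 per group and 40% versus 15%, the standard error is √(0.40×0.60/47 + 0.15×0.85/47) = 0.0884, and 0.25 ± 1.96×0.0884 gives 7.7% to 42.3%. This matches the stated 8%-42%. Reading the 25% reduction as relative (40% to 30%) would give -9% to 29%, which does not match.

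**Size of the delirious subset.** Control: 0.40×47 = 18.8, about 19. Intervention: 0.15×47 = 7.05, about 7. At 52 per group the numbers are 20.8 and 7.8. With 19 and 7 patients, the difference detectable with 80% power is (1.96+0.84)×√(1/19+1/7) = 1.24 SD.

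**Effect of selection.** The documents give no episode lengths, so these are assumptions. Let prevented episodes have lasted *s* days and the remaining ones *l* days, with no effect on any episode that still occurs. At 40% to 15%:

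- control mean among the delirious = (0.25*s* + 0.15*l*)/0.40
- intervention mean among the delirious = *l*
- all-patient means (zero days if no delirium) = 0.25*s* + 0.15*l* versus 0.15*l*

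For *s* = 2 and *l* = 4, the delirious-only means are (0.50+0.60)/0.40 = 2.75 versus 4.00 days, and the all-patient means are 1.10 versus 0.60. The table gives intervention minus control, in days; the last two columns use 0.10 and 0.30 in place of 0.25 and 0.15.

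| *s*, *l* (assumed) | Delirious only, 40% to 15% | All patients, 40% to 15% | Delirious only, 40% to 30% | All patients, 40% to 30% |
|---|---|---|---|---|
| 1, 4 | +1.88 | -0.25 | +0.75 | -0.10 |
| 2, 4 | +1.25 | -0.50 | +0.50 | -0.20 |
| 2, 6 | +2.50 | -0.50 | +1.00 | -0.20 |
| 3, 3 | 0 | -0.75 | 0 | -0.30 |
| 4, 2 | -1.25 | -1.00 | -0.50 | -0.40 |

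The all-patient difference always has the right sign. The sign of the delirious-only difference depends on which episodes are prevented.

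**How often the test would mislead.** In 4,000 simulated trials of the 2-day/4-day case (47 per group, lengths drawn as 1 plus a Poisson count), the two-group comparison among delirious patients was significant in favour of control in about 38% at 40% versus 15%, and in about 12% at 40% versus 30%. With zeros for patients without delirium, it favoured the intervention in about 33% and 7% respectively.

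**Death.** Delirium is measured in the ICU, so the relevant rate is the 1-16% ICU mortality in Section 1. On 18.8 delirious controls this is 0.01×18.8 = 0.2 to 0.16×18.8 = 3.0 deaths. Not all of these need occur while the patient is still delirious or ventilated.

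**ICU discharge.** If measurement ends on leaving the ICU, and exit is independent of resolution at a constant daily rate *h*, a true mean of *m* days is observed as 1/(1/*m* + *h*). For *m* = 5 and assumed *h* of 0.05, 0.10 and 0.20, this gives 4.0, 3.3 and 2.5 days.

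**The case against.** The restriction to delirious patients rests on one sentence in Section 9. Sections 3 and 12 carry no such limit, and Section 13 speaks of the two groups as a whole. If patients without delirium were scored as zero days, the selection problem would disappear. This is correct, and it is why the point is a conflict to be resolved rather than an established restriction. But no section assigns zero days, and Section 9 is the only place that says in whom duration is collected.

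A reader might infer that the plan cuts durations at death and at ICU discharge. The documents state neither; both follow only from the absence of any rule and of any described post-ICU assessment. The outcome is also called ICU delirium, so measurement confined to the ICU may be intended.

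A reader might also take the background figure, "an in-hospital mortality rate of 25% to 33" per cent, and conclude that 5 to 6 of 19 delirious controls (0.25 and 0.33 of 18.8 = 4.7 and 6.2) would have durations cut by death. That does not fit ICU-only measurement, because a death after ICU discharge cannot shorten it. Both mortality ranges come from background literature, not from this unit.

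The inverse-probability-weighted analysis in Section 13 addresses the lack of randomisation. It does not deal with selection by becoming delirious, or with death. Finally, this is a pilot, and duration is secondary and plays no part in the sample size. That limits the stakes without removing the problem.

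**Conclusion.** The concern holds in a limited form. Section 9 conflicts with Sections 3 and 12 on who contributes the secondary outcomes, and Section 13 compares durations by ANOVA with no rule for patients without delirium or for death. If Section 9 is followed, the comparison rests on about 19 versus 7 patients selected by the primary outcome, and its sign can be wrong. At 40% versus 15% the delirious-only difference ranges from +2.50 to -1.25 days over the assumed lengths, while the all-patient difference is negative throughout.

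The documents do not support the stronger conclusion that the intervention will appear to lengthen delirium. That requires the prevented episodes to be the shorter ones, and no episode lengths are given. Misclassification by death is a smaller matter, at most about 0 to 3 delirious controls. An all-patient outcome that accounts for death is better than ANOVA on raw durations and cheap enough to adopt.

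**What to change.** 1. Reconcile Section 9 with Sections 3 and 12 so that delirium duration, ventilation days, length of stay and mortality are collected for all enrolled patients.
2. In Sections 10 and 13, replace ANOVA on raw durations with days alive and free of delirium in the ICU, and days alive and free of ventilation, over a fixed window from enrolment (for example 14 or 28 days), with death in the window scored as the worst value.
3. Compare these by the Mann-Whitney test, which Section 13 already names, and include them in the planned inverse-probability-weighted comparison, stating the weighted statistic to be used.
4. Keep duration among delirious patients as a descriptive summary.
5. Report by group how many patients left the ICU with a positive last CAM-ICU.

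The cost is protocol wording plus a few data items. Section 12 does not list daily CAM-ICU results or dates of death and ICU discharge, so these should be added; they should be available from routine charts. Only in-hospital mortality is collected, so a rule is also needed for patients discharged alive before the window ends.

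Two downsides remain. The new outcome mixes mortality with duration, so mortality should be shown beside it. And because CAM-ICU is described only in the ICU, the change does not remove truncation at ICU discharge: a patient who leaves while still delirious is credited with delirium-free days. The protocol should state that limit, and item 5 shows how large it is.
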